1. PROTOCOL SYNOPSIS

Title	Does Sildenafil Improve Endothelial Dysfunction in Rheumatoid Arthritis?
Short title	SEDRA
Clinical study phase	II
Study objective(s)	The primary objective of this study is to determine whether sildenafil use in rheumatoid arthritis (RA) patients leads to improvement in parameters of vascular function and to confirm its safety profile.
Test drug(s)	Sildenafil
Name of active ingredient	Sildenafil
Dose(s)	50 mg once daily
Route of administration	Oral
Duration of treatment	3 months
Reference drug(s)	Placebo
Name of active ingredient	Not applicable
Dose(s)	Matching placebo tablets to sildenafil 50 mg once daily
Route of administration	Oral
Duration of treatment	3 months
Background treatment	Not applicable
Indication	RA patients with no known history of cardiovascular disease(CVD), but at least one traditional cardiovascular (CV) risk factor in addition to their RA

Diagnosis and main criteria for inclusion	
 a. Meets 2010 American College of Rheumatology (ACR) classification criteria¹ for diagnosis of RA b. Aged 18 years or older c. No known history of CVD (see Exclusion Criteria) d. At least one traditional CV risk factor (i.e., older age [men \geq45 years, women \geq55 years], obesity [defined as body mass index (BMI) $>$30 kg/m²], smoking, hypertension, hyperlipidemia, diabetes mellitus, family history of premature [defined as diagnosed at $<$65 years old] CVD in first-degree relative) e. On stable baseline doses of RA medications, defined as no change in dose within past 4 weeks and no anticipated changes over the next 6 months f. On no higher than 10 mg per day of prednisone or prednisone-equivalent within past 4 weeks g. RA disease duration (from symptom onset) of more than 6 months h. Having clinical disease activity index (CDAI) of $>$2.8 but \leq22 (i.e., either low or moderate disease activity), within 30 days of study enrollment
Study design	6-month prospective phase II, single-center, randomized double-blind, placebo-controlled crossover single-center efficacy trial
Methodology	
This study is designed to investigate the efficacy and safety of sildenafil 50 mg once daily in RA patients with no known history of CVD, but at least one traditional CV risk factor. Patients will be randomized 1:1 to receive either sildenafil or placebo for 3 months, then after a 2-week washout, crossed over to each respective group for an additional 3 months. Vascular studies validated in assessing endothelial dysfunction (brachial artery flow-mediated dilation [FMD]²⁻⁴ and peripheral arterial tone [PAT])⁵ and laboratory studies for selected atherosclerosis biomarkers will be performed at baseline, 3 months pre- and post-washout, and 6 months. Adverse events will be collected to assess sildenafil's safety.

Type of control	Placebo
Number of subjects	Up to 80 randomized subjects (to achieve final total of 60 subjects after expected ~20% drop-out)
Primary variable	Vascular function, determined through brachial arterial flow-mediated dilation (FMD) and peripheral arterial tone (PAT)
Plan for statistical analysis	
For the primary variable, treatment group (sildenafil vs. placebo) is the exposure of interest, with vascular function measures: (1) percent increase in mean maximum brachial artery diameter (%BAD) using FMD (continuous), and (2) mean PAT ratio (continuous) using EndoPAT 2000, as the primary outcomes of interest (measured at 0, 3 months pre- and post-washout, and 6 months). Given the cross-over design, analyses will focus on within-subject comparisons of sildenafil versus placebo periods. All tests will be 2-sided with $\alpha=0.05$. The analysis will use linear mixed models⁶, with a term for treatment order (i.e. randomized initially to sildenafil or placebo), to assess whether %BAD and mean PAT ratio differ significantly between the sildenafil and placebo periods within subjects, adjusting for treatment order and CVD risk factors, baseline RA and CV medication use, disease activity (CDAI) and duration, and baseline levels of %BAD and PAT. Secondary outcomes of interest for Specific Aim 1 are the frequencies of AEs and SAEs. Since the absolute numbers of these events is anticipated to be small, Fisher's exact tests will be used to compare these frequencies between the initial sildenafil and placebo groups.

List of abbreviations

ACE	angiotensin-converting enzyme
ACR	American College of Rheumatology
AE	adverse event
AIDS	acquired immunodeficiency syndrome
ALT	alanine aminotransferase (also known as SGPT, qv)
AST	aspartate aminotransferase (also known as SGOT, qv)
ARB	angiotensin receptor blocker
AUC	area under the plasma concentration versus time curve
BAD	brachial artery diameter
BMI	body mass index
BP	blood pressure
CAD	coronary artery disease
cAMP	cyclic adenosine monophosphate
CCP	anti-cyclic citrullinated peptide antibody
CDAI	Clinical Disease Activity Index
CD40L	CD40 ligand
cGMP	cyclic guanosine monophosphate
CI	confidence interval
CRF	case report form
CRP	C-reactive protein
CV	cardiovascular
CVD	cardiovascular disease
DAS28	Disease Activity Score-28
DM	diabetes mellitus
DMARDs	disease modifying antirheumatic drugs
ECG	electrocardiogram
ED	erectile dysfunction
ELISA	enzyme linked immunosorbent assay
ESR	erythrocyte sedimentation rate
FMD	flow-mediated dilation
g	gram
GFR	glomerular filtration rate
HDL	high density lipoprotein
HIPAA	Health Insurance Portability and Accountability Act of 1996
HIV	human immunodeficiency virus
HOMA-IR	homeostatic model assessment of insulin resistance
HR	heart rate
HRQoL	health-related quality of life
hsCRP	high-sensitivity C-reactive protein
HTN	hypertension
ICAM	intracellular adhesion molecule
IDS	Investigational Drug Service
IL	interleukin
IRB	Institutional Review Board
ITT	intent to treat

kg	kilogram
L	liter
LDL	low density lipoprotein
LFTs	liver function tests
Lp(a)	lipoprotein(a)
MD	medical doctor
mg	milligram
ml	milliliter
mmHg	millimeters of mercury
MMP	matrix metalloproteinase
MOOP	manual of operations and procedures
MPO	myeloperoxidase
NIAMS	National Institute of Arthritis and Musculoskeletal and Skin Diseases
NO	nitric oxide
NSAIDs	nonsteroidal anti-inflammatory drugs
OHRP	Office of Human Research Protections
PAH	pulmonary arterial hypertension
PAT	peripheral arterial tone
PDE	phosphodiesterase
PDE5	phosphodiesterase 5
RAPID-3	Routine Assessment of Patient Index Data-3
RDMS	Rheumatic Disease Management System
RF	rheumatoid factor
RHI	reactive hyperemia index
SAE	serious adverse event
SAP	statistical analysis plan
SBP	systolic blood pressure
SD	standard deviation
UPMC	University of Pittsburgh Medical Center
VCAM	vascular cell adhesion molecule

2. INTRODUCTION

2.1 Background

2.1.1 CARDIOVASCULAR RISK AND ENDOTHELIAL DYSFUNCTION IN RA

- Cardiovascular Risk in RA is Increased, Yet Primary CVD Preventive Care in RA is Lacking

We and others have previously shown that rheumatoid arthritis (RA) is independently associated with an approximately 2-fold increased risk of cardiovascular disease (CVD). Indeed, RA itself is deemed to impart a cardiovascular (CV) risk equivalent to diabetes mellitus (DM). However, unlike in DM, little is known about optimal adjunctive primary and secondary CV prevention strategies for the RA population. Inflammation is known to contribute to CVD risk in RA. Multiple studies show that disease modifying anti-rheumatic drugs (DMARDs) and biologic agents (e.g., tumor necrosis factor [TNF]- α inhibitors) can partially mitigate the increased CVD risk in RA patients. The importance of using these drugs to control inflammation early in RA is well recognized, both for reducing joint damage and long-term CVD risk. However, despite early use of these drugs to treat RA, the mortality gap in RA patients compared to the general population is still widening, in part due to suboptimal primary and secondary CVD preventive care in RA. Furthermore, negative side effects of DMARDs and biologic agents hinder their use as adjunctive primary CVD prevention strategies.

- RA Patients Experience Unique Barriers to Traditional CVD Preventive Care Strategies

In a review of statins and CVD risk in RA, it was noted that statins may be beneficial in primary (but not secondary) CVD prevention in RA. However, they cause more musculoskeletal and gastrointestinal side effects in RA patients than the general population, which limits their routine use. Similarly, pain and fatigue in RA patients limit their abilities to enact lifestyle changes (e.g., exercise) that are well-known to improve CV risk.

- Endothelial Dysfunction: An Important “First Step” in Atherosclerosis and CV Risk in RA

One of the most important early steps of atherogenesis is endothelial dysfunction, which also contributes to the progression of atherosclerotic plaque. The fundamental feature of endothelial dysfunction is impaired nitric oxide (NO) bioavailability, resulting in an impaired ability of the artery to dilate in response to physical and chemical stimuli. NO exerts cardioprotective roles by relaxing smooth muscle cells of the vessel wall, preventing leukocyte migration, adhesion molecule (e.g., vascular cell adhesion molecule [VCAM]-1, intercellular adhesion molecule [ICAM]-1) expression, and platelet aggregation. The degree of endothelial dysfunction has been shown in numerous clinical studies in other

high-risk populations to be closely associated with increased risk of future CVD events and adds prognostic value beyond traditional CV risk factors. Specifically, a recent prospective study of 528 stable patients at high risk of CVD events showed that advanced endothelial dysfunction significantly correlated with near future CVD events, and adding a physiological measure of endothelial dysfunction to other risk classification models (e.g., Framingham score, angiographic scoring system, etc.) could be clinically valuable in identifying vulnerable patients.

- Endothelial Dysfunction is Increased in RA Patients

Recent studies have shown that atherosclerosis lesions occur earlier and have a more rapid evolution in RA patients than the general population. In mouse models of collagen-induced arthritis, the severity of endothelial dysfunction mirrored the arthritis severity. In observational human studies, subclinical atherosclerosis and endothelial dysfunction increased in early RA patients and RA patients without CVD risk factors or complications compared to controls.

- Endothelial Dysfunction in RA: Both Inflammation and Traditional CVD Risk Factors Are Important

In RA, both traditional CVD risk factors and markers of RA severity contribute to models predicting CVD events. Recent studies showed abnormal endothelium-independent microvascular function that correlates with inflammation, but is not altered by short-term anti-inflammatory therapy. Classical CVD risk factors and anti-tumor necrosis factor (TNF)- α medications have different effects on micro- and macrovascular endothelial function, suggesting combined CVD prevention approaches (i.e., treating both inflammation and classical CVD risk-related endothelial dysfunction) may be necessary.

- Biomarkers of Endothelial Dysfunction in RA Correlate with Subclinical Atherosclerosis

Biomarkers of endothelial dysfunction are significantly higher in RA patients than controls, even after controlling for medication use or traditional CVD risk factors. VCAM-1 has been associated with common carotid artery intima-media thickness (cIMT) as determined by carotid ultrasonography (US), a measure of subclinical atherosclerosis. In preliminary studies from my current NIH K23 award (K23 AR061407), we have similarly found in a cross-sectional analysis that markers of endothelial dysfunction (ICAM-1, VCAM-1, and E-selectin) were significantly positively associated with cIMT in 46 RA subjects and 70 controls, both overall and in the RA group alone.

- Predictors of Endothelial Dysfunction in RA - Inflammatory Markers and Higher Disease Activity

Sarli et al investigated predictors of endothelial dysfunction (as measured by brachial artery FMD) in patients with RA in a case-control study, and found RA patients had significantly more endothelial dysfunction than controls. Erythrocyte sedimentation rate (ESR), disease duration, and disease activity score in 28 joints (DAS28) were independent predictors of impaired FMD in RA.

2.1.2 SILDENAFIL

- Sildenafil is a Well-Suited Agent Targeting Endothelial Dysfunction

Drugs that improve endothelial dysfunction hold promise for preventing CVD. Sildenafil, which has been used to treat erectile dysfunction (ED) and pulmonary arterial hypertension (PAH), enhances NO signaling by inhibiting phosphodiesterase-5 (PDE5). (Figure 1) In a mouse model of atherosclerosis, sildenafil restored endothelial function by reducing oxidative stress and plaque deposition in the aorta. Sildenafil has a shorter half-life (4 hours) than other PDE5 inhibitors (e.g., tadalafil or vardenafil), making it well-suited for a crossover study by minimizing potential carryover effects. In pharmacodynamics studies, the effect of sildenafil on erectile response showed diminished response at 4 hours compared to 2 hours, and the effect on blood pressure in healthy volunteers was not different than placebo at 8 hours, irrespective of dosage. Notably, in previous PAH trials, there was significant clinical worsening in PAH after a 2-week washout of sildenafil.⁵¹ It is likely that sildenafil's effects on the brachial vasculature would be similar to other vascular beds. Hence, the short drug activity effects (up to 8 hours) is unlikely to pose significant carryover effects.

[figure not shown]

Figure 1

- PDE Inhibitors Have Pleiotropic Beneficial Effects and Immunomodulatory Properties

PDE5 inhibitors like sildenafil have been shown to improve endothelial function in patients with PAH and DM. They have also been found to have pleiotropic beneficial effects and were safe and well-tolerated over long-term use in patients with ED coexistent with multiple other CV comorbidities. In studies of patients with ED and stable CAD, sildenafil at doses of 50 mg to 100 mg while off nitrates improved cardiac function significantly more than placebo. Phosphodiesterases (PDE) and their substrates (e.g., cAMP and cGMP) are ubiquitously expressed in the immune system. PDE inhibition exerts anti-inflammatory activity by increasing intracellular cAMP. PDE4 inhibitors have efficacy in

experimental autoimmune encephalomyelitis (EAE), a model for multiple sclerosis. Dual PDE4 and PDE7 inhibitors decreased the severity of collagen induced arthritis (CIA) in a rat model of RA. The PDE4 inhibitor apremilast was shown in a phase 2 clinical trial in Behcet's disease and phase 3 human randomized controlled clinical trials in psoriatic arthritis to be effective, safe, and well-tolerated. Both psoriatic arthritis and Behcet's are also systemic autoimmune diseases like RA. PDE5 inhibitors like sildenafil also have immunomodulatory actions, though human studies to date have primarily focused on end-organ manifestations of autoimmune diseases like PAH, Raynaud's phenomenon, renal disease (e.g., IgA nephropathy), and pulmonary fibrosis. Although sildenafil is much more selective for PDE5 (4,000-fold), it also has >700-fold selectivity for PDE4 and other PDEs; hence, it is promising as a potential agent to target not only endothelial dysfunction but inflammation in patients with RA.

3. Study Drug

3.1 Mechanism of Action

Sildenafil is a phosphodiesterase-5 (PDE5) inhibitor. PDE5 normally breaks down the intracellular second messenger of NO, cGMP. Hence, PDE5 inhibition by sildenafil results in increased cGMP and improved endothelial function, with vascular smooth muscle cell relaxation. Sildenafil has a shorter half-life (4 hours) than other PDE5 inhibitors (e.g., tadalafil or vardenafil), making it well-suited for a crossover study by minimizing potential carryover effects. In pharmacodynamics studies, the effect of sildenafil on erectile response showed diminished response at 4 hours compared to 2 hours, and the effect on blood pressure in healthy volunteers was not different than placebo at 8 hours, irrespective of dosage. Notably, in previous PAH trials, there was significant clinical worsening in PAH after a 2-week washout of sildenafil. It is likely that sildenafil's effects on the brachial vasculature would be similar to other vascular beds. **Hence, the short drug activity effects (up to 8 hours) is unlikely to pose significant carryover effects.**

3.2 Rationale

Rheumatoid arthritis (RA), a chronic inflammatory disorder affecting the joints, is associated with a 2-fold increased risk of cardiovascular disease (CVD) and sudden death, which is not explained by traditional cardiovascular (CV) risk factors alone. CVD is a strong contributor to excess morbidity and

mortality in RA, and is likened to an extra-articular disease manifestation akin to a “rheumatoid vasculopathy.” Indeed, RA itself imparts a CV risk equivalent to diabetes mellitus (DM). It is well-recognized that chronic inflammation contributes to CVD risk in RA patients. Studies show that early tight control of disease activity in RA reduces disability and long-term CVD risk. Yet, despite early treatment for RA, the mortality gap in RA compared to the general population is still widening, in part due to suboptimal primary and secondary CVD preventive care in RA. Hence, besides early tight disease control in RA, **attention must now shift to adjunctive primary prevention strategies to mitigate CVD risk in these high-risk patients.** To date, there are no published controlled intervention trials for primary CV prevention in RA, despite this clearly urgent unmet need. The only such trial, TRACE-RA (a placebo-controlled double-blind primary CVD prevention trial in RA with atorvastatin) was stopped prematurely due to low numbers of CVD events that occurred, underscoring the need for use of subclinical CVD endpoints rather than hard CVD events in such trials.

One of the early stages of atherosclerosis is endothelial dysfunction, which is closely associated with risk of future CVD. Using drugs to target endothelial dysfunction is a promising novel strategy for CVD prevention. In RA, inflammation mediates premature endothelial dysfunction by activation of endothelial cells. The fundamental feature of endothelial dysfunction is impaired nitric oxide (NO) bioavailability. NO exerts cardio-protective roles by relaxing vascular smooth muscle cells and preventing leukocyte adhesion. Sildenafil, which is used to treat erectile dysfunction (ED) and pulmonary arterial hypertension (PAH), enhances NO signaling by inhibiting phosphodiesterase-5 (PDE5). In an experimental mouse model of atherosclerosis, sildenafil restored endothelial function, with a 40% decrease in aortic plaque. In human studies, PDE5 inhibitors including sildenafil improved endothelial function in PAH and DM, and were safe and well-tolerated in those with CV co-morbidities. Sildenafil’s favorable safety profile has been studied longer than any other PDE5 inhibitor. Furthermore, PDE inhibitors have immunomodulatory properties that hold promise in treating autoimmune conditions like RA.

Predictors of endothelial dysfunction in RA include markers of inflammation and higher disease activity. In RA, abnormal microvascular endothelial function correlated with inflammation, but was not altered by short-term anti-inflammatory therapy; hence, combined CVD-prevention approaches beyond anti-inflammatory therapy may be necessary. In light of this background, **our central hypothesis is that**

sildenafil, by targeting endothelial dysfunction, may be a uniquely suited agent and novel adjunctive primary CVD prevention strategy in RA. Specifically, our goal is to determine if sildenafil use in RA patients improves endothelial dysfunction, inflammation, and atherosclerosis biomarkers.

4. Risk-Benefit assessment

4.1 Benefits of Study in General:

The benefits from the results of this study will assist in determining whether sildenafil improves endothelial function in RA, which may be important in arresting one of the first steps in the pathogenesis of atherosclerosis and development of future CVD events in RA. Such knowledge may result in a better understanding of the disease process and ultimately may lead to new adjunctive primary preventive and therapeutic approaches for cardiovascular risk associated with RA.

4.2 Potential Risks of Study in General:

Common side effects of the vascular studies (occurring in less than 25% of patients) include discomfort, numbness, or pain from the blood pressure cuff occluding the subject's arm. The EndoPAT and flow mediated dilation tests will be done together at the same time. The subjects will be asked to lie still on their back during the tests; this could cause stiffness, back pain or dizziness. During the tests, the occlusion cuff that will be placed on the subject's arm will stay inflated for 5 minutes. The cuff will squeeze the arm tightly; this could cause minor pain, possible bruising, numbness, tingling and irritation to the skin. If the subject experiences pain or numbness that is bothersome, s/he will be asked to alert the technician performing the test. During the EndoPAT test the finger probes will fit snugly over the index fingers and stay on for about 20 minutes. This could cause numbness, tingling and possible irritation to the skin. Again, if the subject experiences pain or numbness that is bothersome, s/he will be asked to alert the technician performing the test.

Rare study risks (occurring in less than 1% of patients) include minor skin irritations from the ECG leads.

To minimize these risks, a physician and emergency drugs and equipment will be readily available at the VCTRC site where the vascular studies will be performed. Subjects will be asked during and after the

testing how they are feeling and their responses will be noted. The test will be stopped at any point as per the subject's discretion. Subjects will be monitored for gross ECG changes and arrhythmias during the study at all times. Continuous monitoring by pulse oximetry will be maintained during the study. Subjects may be monitored for 30 to 90 minutes after completion of the vascular studies.

There is a small risk that confidentiality may be breached. Data will be kept confidential in a secure database. All forms will be stored in locked filing cabinets. Electronic data will be identified by patient ID only. All computer files will be protected from unauthorized access.

5. STUDY OBJECTIVES

5.1 Primary endpoint

- Specific Aim 1: To determine whether sildenafil use in RA patients leads to improvement in parameters of vascular function; and to confirm its safety profile.

5.2 The Primary Efficacy Outcome measures will be:

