5.2.2 Peripheral Arterial Tone (PAT)

PAT measured by the EndoPAT 2000 device is a non-invasive method to assess endothelial function. It is a standardized, rapid, and easy to apply method, and has been found to correlate with multiple traditional CV risk factors and to be responsive to interventions. PAT is a validated alternative measure to brachial arterial FMD in assessing endothelial function, and is less operator-dependent than FMD. FMD directly measures the dilation capability of the large-conduit artery, whereas PAT measures flow response hyperemia, which is related to endothelial function of small arteries of microcirculation. PAT measures endothelium-mediated changes in vascular tone using bio-sensors placed on fingertips. Changes in arterial tone are elicited by creating a down-stream hyperemic response of the brachial artery from arm occlusion. Contra-lateral arm measurements are used to control for concurrent non-endothelial dependent changes in vascular tone. The semi-automatically calculated result is an index of endothelial function.

5.2.3 Safety Profile: Adverse Event Outcomes:

All adverse event (AE) and serious adverse event (SAE) data will be collected by separate study personnel from those collecting other outcomes; we will document AE and SAE diagnosis, date of onset and resolution, severity, whether it was unexpected or related to intervention; whether the blind was broken; and outcome. Specific AE data will include all common side effects of sildenafil as per Micromedex.

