15.1 Statistical Methods for Specific Aims

For **Specific Aim 1**, treatment group (sildenafil vs. placebo) is the *exposure* of interest, with vascular function measures: (1) percent increase in mean maximum brachial artery diameter (%BAD) using FMD (continuous), and (2) mean PAT ratio (continuous) using EndoPAT 2000, as the *primary outcomes* of interest (measured at 0, 3 months pre- and post-washout, and 6 months). Given the cross-over design, analyses will focus on within-subject comparisons of sildenafil versus placebo periods. All tests will be 2-sided with $\alpha=0.05$.

The analysis will use linear mixed models, with a term for treatment order (i.e. randomized initially to sildenafil or placebo), to assess whether %BAD and mean PAT ratio differ significantly between the sildenafil and placebo periods within subjects, adjusting for treatment order and CVD risk factors, baseline RA and CV medication use, disease activity (CDAI) and duration, and baseline levels of %BAD and PAT. Model fit, appropriate assumptions (e.g. normality, linearity, homoscedasticity), and potential collinearity, will be assessed with standard diagnostic plots and variance inflation factors (VIF). If needed, we will explore corresponding transformations of the covariates, and/or (in the case of collinearity) dropping variables from the model. We will address any non-compliance using an intention-to-treat strategy and will conduct a sensitivity analysis to conservatively assess observing how the worst outcome would affect results. We do not anticipate many will have RA medication changes but those participants will be included in the analysis; a secondary sensitivity analysis will add a covariate (at the corresponding time point(s)) to denote (yes or no) whether medication changed during the course of the study. Although we recognize that different types of medication changes may have

different effects on the outcome, we will not have sufficient power to estimate heterogeneity of effects across different types of medication changes.

Secondary outcomes of interest for Specific Aim 1 are the frequencies of AEs and SAE. Since the absolute numbers of these events is anticipated to be small, Fisher's exact tests will be used to compare these frequencies between the initial sildenafil and placebo groups.

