Potential effect on erectile function is unlikely to be recognized by male subjects unless they already suffer from ED, in which they will likely already be taking PDE inhibitors and will thus be excluded. Further, most RA patients are women. Per Micromedex, headaches were only seen in 21% of ED subjects taking the 50 mg daily dose (vs. 7% in placebo). Although these potential side effects may unblind subjects, the outcome measures in this study (vascular function and serum biomarkers) are unlikely to be affected by subject un-blinding. Different study personnel will collect AE data vs. other outcome data, to minimize risk of un-blinding.

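### The primary objective is partly to confirm safety, but the only planned safety inference is a low-powered Fisher's exact test with no interval and no criterion for confirmation

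*Combined protocol and SAP*

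**What the plan says.** The synopsis objective and Specific Aim 1 (5.1) pair improvement in vascular function with the aim "and to confirm its safety profile". The heading "5.2 The Primary Efficacy Outcome measures will be" covers FMD, PAT and then a third item, "5.2.3 Safety Profile: Adverse Event Outcomes". Elsewhere adverse events (AEs) are not primary: the synopsis and 12.1 name only FMD and PAT, and 15.1 states "Secondary outcomes of interest for Specific Aim 1 are the frequencies of AEs and SAE", as does the synopsis in almost the same words.

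For inference, 15.1 says that Fisher's "exact tests will be used to compare these frequencies between the initial sildenafil and placebo groups". All tests are two-sided at 0.05. The sample size (15.2) rests on %BAD. No power, precision, margin or criterion is given for safety.

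The protocol also cites side effects already known for the drug. Section 15.3.4 says "headaches were only seen in 21% of ED subjects taking the 50 mg daily dose (vs. 7% in placebo"), and the package insert table in 14.9 gives headache 16% vs 4% and flushing 10% vs 1%.

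**The concern.** Confirming a safety profile is a positive claim: it needs evidence that any excess of harm is small. A test of no difference gives that evidence only when it has high power against the excesses that matter, or when an interval shows how large an excess is still compatible with the data. The plan offers neither. If the test is unlikely to detect even a side effect that the protocol itself expects, a non-significant result is uninformative, and one part of the stated primary objective has no analysis that could support it. The efficacy analysis is unaffected.

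**Working it through.** **Inputs.**
- Allocation 1:1 (7.1).
- Up to 80 randomized, so 40 per group (synopsis).
- 60 evaluable, 30 per group (15.2).
- Two-sided test at 0.05 (15.1).
- Headache 21% vs 7% (15.3.4) or 16% vs 4% (14.9). Flushing 10% vs 1% (14.9).
- Assumption: events are counted in period 1 only. Section 15.1 does not say so.

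**The plan's own power figure.** Section 15.2 states 80% power for a paired t-test with n = 60 and effect size 0.37. The noncentrality is 0.37 × √60 = 2.87, the critical t on 59 df is 2.00, and power is 80.5%. The figure reproduces, but it concerns %BAD and says nothing about AEs.

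**Fisher power.** Let X be binomial (n, p on sildenafil) and Y binomial (n, p on placebo), independent. Power is the sum of P(X = x) × P(Y = y) over all tables (x, y) whose two-sided Fisher p-value is at most 0.05.

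| Benchmark | 30 per group | 40 per group |
|---|---|---|
| Headache 21% vs 7% | 19.7% | 33.4% |
| Headache 16% vs 4% | 14.6% | 27.8% |
| Flushing 10% vs 1% | 5.6% | 15.0% |

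The probability of missing the headache excess is therefore 80% or 85% at 30 per group, and 66.6% or 72% at 40 per group. For 80% power, Fisher's test would need about 105 per group (21% vs 7%) or 106 per group (16% vs 4%).

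**Sensitivity to the split.** Fisher's test is discrete, and 80 is not a multiple of the block size of 6, so the arms can differ slightly in size. For 21% vs 7%, the miss probability is 63% with 41 on sildenafil and 39 on placebo, and 59% with 39 and 41. For 16% vs 4% it is 70% and 63%. Two in three is thus an approximate figure for 80 randomized, not a lower limit.

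**What the planned output would hide.** Suppose 8/40 vs 3/40 have headache, close to 21% vs 7%. Fisher's p is 0.19. The Newcombe 95% interval for the difference of 12.5 points runs from about −3 to +28 points. The test says not significant; the interval shows that a large excess is not excluded.

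**Zero events.** With no events among n exposed, the exact two-sided 95% upper limit is 1 − 0.025^(1/n): 4.5% for n = 80 and 6.0% for n = 60. The one-sided 95% bound is 1 − 0.05^(1/n): 3.7% and 4.9%. In the initial sildenafil group alone, the two-sided limits are 8.8% (n = 40) and 11.6% (n = 30).

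**Within-subject comparison.** Exact McNemar power, with the between-period correlation phi assumed to be 0 to 0.4 (the documents give none):

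| Benchmark | 60 subjects | 80 subjects |
|---|---|---|
| Headache 21% vs 7% | 51–73% | 66–88% |
| Headache 16% vs 4% | 48–69% | 65–88% |

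Using both periods helps a good deal, but at 60 subjects it still falls short of 80%. The remedy therefore has to be an interval and a modest claim, not only another test.

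**The case against.** **No passage says that a null test will be read as proof of safety.** That is correct. A reader might infer that the trial is set to report non-significance as confirmation, but this is a prediction, not something the plan states. What stands is narrower: the objective says confirm, and nothing in the analysis section could support that word.

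**Safety does not rest on the test alone.** Also correct. Severity, relatedness and outcome are recorded, 8.4 has withdrawal rules for named events, and serious adverse events (SAEs) go to an independent Safety Officer within 48 hours (14.8.1). These protect subjects and describe events. They do not supply the missing inference.

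**Headache is not a planned test.** Section 15.1 speaks of AE and SAE frequencies in general, and the rates come from ED populations, with as-needed flexible dosing behind the 14.9 table. The power figures are therefore a benchmark. Power for overall AE frequency cannot be computed, because the documents give no rate for it.

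**The ranking looks like a contradiction.** A reader might infer that AEs are primary in one half of the document and secondary in the other. The documents do not support that much: the synopsis, 12.1 and 15.1 agree that AEs are not primary, and a secondary outcome can sit within a primary aim. The outlier is 5.2.3, under a heading about efficacy, and it is most naturally a misplaced subsection.

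**Low power for single AEs is usual in a trial of this size.** True, and it is a reason to plan intervals and a descriptive aim.

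**Conclusion.** The concern holds in this form: the plan sets out to confirm safety, yet its only safety inference is a Fisher test between initial groups, with no interval and no criterion. On the protocol's own benchmark rates, a known headache excess would be missed about two times in three with all 80 randomized, and about four times in five or more with 30 per group. Non-significance cannot carry the word confirm.

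This rests on period 1 counting, on rates borrowed from ED populations, and on headache standing in for AEs generally. If events from both periods were counted by initial group, both groups would have had both treatments and the contrast would be weaker still.

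A reader might go further and say that the miss rate is never below two in three. It is not a strict bound: it is 66.6% at 40/40 and 59% to 63% at splits one subject away. It is a point about the safety claim and its reporting, worth correcting before analysis.

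**What to change.** 1. In the synopsis and 5.1, replace confirm with describe for the safety part of the objective.
2. In 15.1 and the synopsis, make the main safety result the incidence of AEs and SAEs by treatment received over both periods, with exact two-sided 95% confidence intervals and a within-subject (paired) risk difference with its 95% interval. This uses the up to 80 subjects that 7.1 counts on for safety data. Keep Fisher's test on period 1 events as supportive only, and state that a non-significant result is not evidence of safety.
3. If a zero-event limit is quoted, use the two-sided exact upper limit for the number actually exposed (4.5% for 80, 6.0% for 60) so that it agrees with the tables, or label 3.7% and 4.9% as one-sided 95% bounds. With about 20% dropout expected, fewer than 80 may receive sildenafil.
4. Move 5.2.3 out from under the primary efficacy heading, to agree with the synopsis, 12.1 and 15.1.

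The cost is wording in four places and a few table columns, with no new subjects, visits or data. The downside is a more modest safety claim.
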